7.4.2 Analysis

Descriptive summary statistics by analysis visit and treatment group will be provided for observed values and, when reported at baseline and post-baseline, absolute changes from baseline by category (hematology/coagulation, chemistry, urinalysis) and by parameter. Data are displayed in SI units as provided by the central laboratory.

Urine pregnancy test results will be listed.

Treatment-emergent laboratory abnormalities are summarized by laboratory category, variable and severity over the on-treatment period.

For each lab category, a listing of the value at each time point, in SI Units, for all variables and the changes from baseline (continuous and categorical) as well as the abnormality grade/flag will be produced and will include all visits. The values not considered in the analyses, i.e., local laboratories, will be flagged.

7.5 Electrocardiography analysis

The analysis will be performed on the following variables:

- Treatment-emergent ECG abnormalities (i.e., with onset from time of study drug administration and up to 48 hours after and, not present at baseline),
- Absolute change from baseline to each time point in ECG variables: HR, and the intervals PQ/PR, QRS, QT, RR, QT corrected with Bazett's formula (QTcB) and QT corrected with Fridericia's formula (QTcF).

The absolute value and absolute change from baseline to each time point will be summarized.

Incidence of subjects with at least one marked abnormality across all ECG variables and by ECG variable will be provided overall (worst value), and for each of the three time points: pre-dose, at 1 hour and at 24 hours post study administration.

ECG marked abnormalities are defined for QT, QTcF and QTcB (msec), for the different cases:

1. Value > 450 ms for men,
2. Value > 470 ms for women,
3. Value > 500 ms regardless of gender,
4. Absolute change from baseline > 30 ms regardless of gender,
5. Absolute change from baseline > 60 ms regardless of gender

In addition, the treatment-emergent ECG findings, i.e., findings related to an ECG assessment occurring during on-treatment period and absent at baseline, are tabulated by

overall interpretation (normal, abnormal), by category (e.g., rhythm, ST segment) and treatment group.

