10.2.3.3 ECG

ECG recording is performed at the time points described in [Table 3](#).

- Treatment-emergent ECG abnormalities (i.e., up to 48 h after study treatment administration).
- Absolute change from baseline to each time point in ECG variables: HR, and the intervals: PQ/PR, QRS, QT, RR, QTcB, and QTcF.

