10.3.4.4 Electrocardiograms

Each ECG summary and listing will include unscheduled assessments.

The absolute change from baseline to each time point for ECG variables will be summarized. The absolute values at each time point will be summarized.

Number (%) of subjects having a marked ECG abnormality during the treatment period will be summarized.

All ECG values for subjects with at least one marked ECG abnormality will be listed.

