10.2.2 Baseline

Baseline is the last non-missing assessment performed or value measured before or on the day and time of study drug administration (i.e., prior to treatment administration), unless otherwise defined in the specific analysis section.

Subjects without any data for a parameter before treatment administration will have a missing baseline (and therefore a missing change from baseline) value for this parameter.

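### The overall row for marked QT/QTc abnormalities in SAP 7.5 is not limited to post-dose ECGs and has no baseline exclusion on the absolute thresholds, so it does not deliver the treatment-emergent count (minor)

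*SAP*

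**What the plan says.** SAP 7.5 names treatment-emergent ECG abnormality as an analysis variable, defined as "with onset from time of study drug administration and up to 48 hours after and, not present at baseline". It then plans the incidence of subjects with at least one marked abnormality, across all ECG variables and by variable, "overall (worst value), and for each of the three time points: pre-dose, at 1 hour and at 24 hours post study administration".

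Marked abnormality is defined for QT, QTcF and QTcB by five cases:

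- Cases 1 to 3 are absolute: "Value > 450 ms for men", then 470 ms for women and 500 ms for either sex.
- Cases 4 and 5 are changes: "Absolute change from baseline > 30 ms regardless of gender", then the same with 60 ms.

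A further table, by overall interpretation and finding category, is restricted to "findings related to an ECG assessment occurring during on-treatment period and absent at baseline". SAP 10.2.2 states: "Baseline is the last non-missing assessment performed or value measured before or on the day and time of study drug administration". The pre-dose ECG is therefore normally the baseline.

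Protocol 6.3 makes treatment-emergent ECG abnormalities a safety endpoint, and Protocol 10.2.3.3 words the variable as "Treatment-emergent ECG abnormalities (i.e., up to 48 h after study treatment administration". For the marked abnormalities Protocol 10.3.4.4 says: "Number (%) of subjects having a marked ECG abnormality during the treatment period will be summarized".

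**The concern.** The section defines an emergent abnormality by two conditions, onset after dosing and absence before it. The sentence that plans the QT/QTc threshold table repeats neither. Pre-dose is one of the three time points named next to the worst-value row, and cases 1 to 3 can be met on a pre-dose ECG. By contrast, SAP 7.4.1 and 7.4.2 apply both conditions to laboratory abnormalities.

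Protocol 1.5.1 describes this as the first study of the drug in patients, and this table is its categorical QT display. If the overall row mixes long-standing prolongation with new prolongation, it does not estimate the stated endpoint, and two programmers could produce different counts from the same text. The marginal counts at pre-dose, 1 h and 24 h do not resolve this, because they do not show which subjects are newly abnormal.

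**Working it through.** The plan states no ECG rate, so there is no figure to reproduce. The check is first textual, then illustrative.

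**1. Who enters each possible row (absolute thresholds, cases 1 to 3)**

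| Subject | Worst of all three ECGs | Worst of post-dose ECGs | Treatment-emergent |
|---|---|---|---|
| Above pre-dose, normal after | counted | not counted | not counted |
| Above pre-dose and after | counted | counted | not counted |
| Normal pre-dose, above after | counted | counted | counted |

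The SAP text permits the first column and nowhere states the third for these thresholds. Cases 4 and 5 are relative to baseline, so prolongation already in the baseline value does not trigger them.

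**2. Size within an arm**

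All rates here are assumed. The arm size of 108 is from Protocol 10.5. Let q be the share above the threshold pre-dose, r the share of those still above it afterwards, and a the new post-dose incidence in the rest.

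- All ECGs: q + (1 − q)a
- Post-dose only: qr + (1 − q)a
- Treatment-emergent: (1 − q)a

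For q = 5%, r = 80%, a = 2%:

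- All ECGs: 0.05 + 0.95 × 0.02 = 0.069, × 108 = 7.5
- Post-dose only: 0.04 + 0.019 = 0.059, × 108 = 6.4
- Treatment-emergent: 0.019 × 108 = 2.1
- Pre-existing share of the all-ECG count: 0.05 / 0.069 = 72%

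Subjects per 108 with r = 80% and a = 2%:

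| q | All ECGs | Post-dose only | Treatment-emergent | Pre-existing share of all-ECG count |
|---|---|---|---|---|
| 2% | 4.3 | 3.8 | 2.1 | 51% |
| 5% | 7.5 | 6.4 | 2.1 | 72% |
| 10% | 12.7 | 10.6 | 1.9 | 85% |
| 20% | 23.3 | 19.0 | 1.7 | 93% |

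With a = 5% the pre-existing share runs from 29% (q = 2%) to 83% (q = 20%). Dropping the pre-dose ECG removes only q(1 − r). The baseline condition removes the rest.

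**3. Cross-check by simulation**

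Assumed for men with no drug effect: QTcF mean 410 or 420 ms, between-subject and within-subject SD of 20 and 10 or 22 and 12 ms, three ECGs, threshold 450 ms. Over the four combinations:

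- any ECG above threshold: 7.0% to 20.2%
- treatment-emergent: 3.3% to 8.6%
- counted on the pre-dose ECG alone: 1.4% to 3.4% of all subjects
- share of those counted who were already above pre-dose: about 53% to 57%

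**4. Between arms**

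Randomization gives the same expected q in each arm. The expected difference in the all-ECG row is [q + (1 − q)a₁] − [q + (1 − q)a₀] = (1 − q)(a₁ − a₀). That is slightly less than a₁ − a₀, and equals the difference in treatment-emergent counts over all subjects. The relative contrast and the precision suffer more. With q = 5%, a₁ = 5%, a₀ = 2%:

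- All ECGs: 9.75% v 6.9%, difference 2.85 points, ratio 1.41, SE √[(0.0975 × 0.9025 + 0.069 × 0.931)/108] = 3.8 points
- Treatment-emergent: 4.75% v 1.9%, difference 2.85 points, ratio 2.5, SE √[(0.0475 × 0.9525 + 0.019 × 0.981)/108] = 2.4 points

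**The case against.** The strongest reply is that the text never says the worst value is taken over all three ECGs. The time points belong to the by-time-point display, and the overall row could be post-dose only. This stands as far as it goes: inclusion of pre-dose is the natural reading, not an express statement. But nothing excludes it, and a post-dose-only row would still count persistent prolongation.

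A reader might infer that the SAP passes off pre-existing prolongation as an on-treatment finding. The documents do not support that. The row is not labelled on-treatment or treatment-emergent, and pre-dose has its own line.

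A reader might also infer a flat contradiction of Protocol 10.3.4.4. That is not clear either. Protocol 3.1.1 defines the treatment period as Day 1 and Day 2, and Day 1 includes the pre-dose ECG. It is SAP 2.3 that starts the on-treatment period at dosing. The firmer mismatch is with the treatment-emergent definition in SAP 7.5 and Protocol 10.2.3.3.

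It is fair to add that the treatment-emergent variable heads SAP 7.5, that changes from baseline are summarized at each time point, that the 1 h and 24 h rows are post-dose, and that Protocol 10.3.4.4 lists all ECG values for subjects with a marked abnormality. These limit the harm, but none supplies an absolute-threshold count of new cases. The table shells and the separate list of outputs (SAP 8.1.2 and 12) were not available. They might define the row, but that cannot be assumed.

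**Conclusion.** The point holds as a minor correction to a descriptive safety table. As written, no QT/QTc absolute-threshold row delivers the plan's own treatment-emergent definition, and the overall row naturally takes in subjects already above a threshold before dosing.

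The consequence is an inflated count in every arm and a slightly diluted, noisier contrast. It is not a bias toward one arm. The claim that a QTc effect would be concealed goes too far, given the change-from-baseline criteria and summaries. The claim that the row would mostly describe the population before dosing holds only under some assumed rates: the pre-existing share runs from 29% to 93% in the illustration. All magnitudes rest on assumed ECG rates or distributions, because the documents give none. The primary PD conclusion is untouched.

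**What to change.** In SAP 7.5:

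- Take the overall worst value from post-dose ECGs within the 48 h on-treatment period.
- For the absolute thresholds, count a subject as treatment-emergent only if that threshold was not already exceeded at baseline. Show those already above it separately, for example in a shift table.
- Keep pre-dose as a descriptive line that does not feed the overall row.
- Leave cases 4 and 5 as they are.

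Both of the first two changes are needed, since removing the pre-dose ECG alone leaves persistent prolongation in the count. The cost is one SAP sentence and a filter in one table, plus the separate display of subjects already above threshold. All of it comes from ECGs already planned, so no new data are needed.

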7.6 Vital signs and body weight

7.6.1 Blood pressure and pulse analysis

This includes the systolic and diastolic blood pressures (sitting and/or supine), and pulse rate.

Systolic and diastolic blood pressures will be summarized regardless of the subject position at time of measure.

A listing of the value at each visit, in SI units, for all variables and the changes from baseline (continuous and categorical) as well as the abnormality grade/flag is produced and includes all visits. The values not included in the analyses are flagged.

For each parameter at each time point over the course of the study, quantitative descriptive statistics for the value at the visit and the change from baseline are presented by parameter, by time point and treatment group.

The evolution of systolic and diastolic blood pressures values over time will be provided graphically by visit using box-and-whisker plots visualizing mean, median, interquartile ranges, SD, and outliers.

The number and percentage of subjects with at least one marked abnormality for blood pressure is provided by visit / time point and treatment group.

7.6.2 Body weight, and other vital sign analyses

Body weight values and assessment date will be listed.

7.7 Other safety variables and analyses

Not applicable.

8 GENERAL STATISTICAL METHODOLOGY

Data will be analyzed using SAS version 9.3 or higher.

8.1 General rules for data presentations

General rules for data presentations as described here are followed unless otherwise specified.

Data are listed and summarized by descriptive statistics (tables or figures) as described below.

8.1.1 Treatment groups

The study included the following 8 *randomization groups* corresponding to the combination of the four study treatment groups (i.e., ACT-246475 8 mg, ACT-246475 16 mg, and their matching placebos) and two injection sites (thigh and abdomen).

The main purpose of this randomization strategy was to balance treatment as well as site of injection assignment. For the analysis, the study treatment arms will consist of the treatment arms: *Placebo*, *ACT-246475 8 mg*, and *ACT-246475 16 mg*. The placebo treatment arm combines the two placebo dose-matching groups.

All analyses, unless stated otherwise, will be reported by those 3 treatment arms, and in this order.

In all Tables, Figures and Listings, treatment groups will be labeled using treatment label [last column of [Table 6](#)].

Table 6 Randomization groups and treatment group labels

Randomization groups		Treatment groups (labels for outputs)
Treatment	Injection site	
ACT-246475 8 mg	Thigh	ACT-246475 8 mg
ACT-246475 8 mg	Abdomen	
ACT-246475 16 mg	Thigh	ACT-246475 16 mg
ACT-246475 16 mg	Abdomen	
Placebo matching ACT-246475 8 mg	Thigh	Placebo
Placebo matching ACT-246475 8 mg	Abdomen	
Placebo matching ACT-246475 16 mg	Thigh	
Placebo matching ACT-246475 16 mg	Abdomen	

Some analyses may require displaying some of the following groups: *Screened failure* subjects group, *Total randomized* (i.e., any subject who has been assigned a study treatment), *Total ACT-246475* group (i.e., subjects randomized to either ACT-246475 8 or 16 mg arms), and *Total* (i.e., all subjects screened).

The order of the treatment group in the statistical report, would then be: Screened failures, ACT-246475 8 mg, ACT-246475 16 mg, Total randomized, Total ACT-246475, and Total.

8.1.2 Descriptive statistics

Descriptive statistics will be provided by treatment group (and all pooled groups for study subjects analyses) depending on the nature of the criteria:

Quantitative:

Number of observed values, number of missing values, mean, SD, minimum and maximum, median, 1st and 3rd quartiles.

Qualitative:

Number of observed values, number of missing values, number and percentage of subjects per level/category.

Unless otherwise specified in the table shells, the percentage calculation will not consider missing values in denominators.

The number of missing values is displayed only if > 0 . For continuous variables, it is displayed after the number of non-missing observations, for categorical variables after the last category (no percentage reported).

Listings are grouped by treatment arm (same order as in tables headers, if applicable, screening failures are listed last), subject identification number and assessment date as applicable.

Raw data listings, if required, are based on datasets as received. All data collected are displayed, including unscheduled visits (if any).

8.2 Efficacy analyses

Not applicable.

9 INTERIM ANALYSES

Not applicable.

10 GENERAL DEFINITIONS AND DERIVATIONS

10.1 Analysis periods and visit windows

The on-treatment period is defined as the period starting from study drug administration up to 48th hour post administration. However, some assessments will not have the exact time, only the day. In this case it will be assumed that the 48 hours on-treatment period corresponds to the day of study drug administration and to the two following days (1st, 2nd and 3rd day of the on-treatment period).

This results in an over-estimated duration of the on-treatment period for those events that do not have assessment time.

10.2 Dates, times and days

10.2.1 Definition of study start

Study start day is the day of informed consent signature.

10.2.2 Baseline

Baseline is the last non-missing assessment performed or value measured before or on the day and time of study drug administration (i.e., prior to treatment administration), unless otherwise defined in the specific analysis section.

Subjects without any data for a parameter before treatment administration will have a missing baseline (and therefore a missing change from baseline) value for this parameter.

10.2.3 Post-baseline assessment

Post-baseline assessment is any assessment performed after baseline and up to EOS.

10.2.4 Treatment start date/time

It is the date/time recorded in the ‘Study Treatment Administration’ eCRF page.

10.2.5 Definition of end of study treatment

Not applicable (study treatment is injected only once).

10.2.6 Definition of End-of-Study

EOS is defined as the day of the 30-day safety follow-up telephone call.

For randomized subjects who never received the study treatment, EOS date is defined as the earliest date amongst the following dates, as reported in the “Study Discontinuation” eCRF page:

1. Date of last successful contact,
2. Date of subject decision,
3. Date of physician decision,
4. Date of subject death
5. Date subject was informed of sponsor’s decision.

10.2.7 Definition of screening failure

A subject is considered a screening failure if he/she was not randomized (i.e., has not been assigned a study drug).

10.2.8 Definition of premature study discontinuation

Subjects are considered to have prematurely discontinued the study if a reason for stopping the study is provided in the Study Discontinuation eCRF page.

The date and the reason for study discontinuation are collected in the “Study Discontinuation” form (and in the “Death” form if the subject died).

10.3 Definition of reason for screening failure

For subjects who are considered a screening failure, the reason for screening failure used in the analysis is the last reported one.

10.4 Convention for demography data considered for analysis when multiple values reported

For subjects with multiple baseline assessment (multiple screening attempts), the last values are displayed and included in any analysis, while prior ones will only be presented in listings.

10.5 Coding dictionaries

The most recent version of MedDRA dictionary implemented in Idorsia at time of database closure will be used for coding medical history, and AEs. The version will be displayed in statistical outputs footnotes.

Similarly, the most recent version of the WHO Drug Reference Listing dictionary based on WHO Anatomical Therapeutic Chemical (ATC) classification system implemented in Idorsia at time of database closure will be used for coding of previous and concomitant therapies reported in this trial.

10.6 Medical history and current (study concomitant) medical conditions

Medical history and current medical conditions, i.e., study concomitant medical conditions, at baseline include previous and/or concomitant procedures or diagnoses recorded on the ‘Medical History’ and ‘Specific Medical History’ eCRF pages.

Medical history are those procedures or diagnoses for which

1. The end date of the procedure or diagnosis is not missing and is earlier to the study treatment administration date.

OR

2. The end date of the procedure or diagnosis is missing and Question ‘Ongoing at Informed Consent signature?’ in the ‘Medical History’ eCRF page is answered as ‘No’

If neither applies, all other procedures and diagnoses are considered *Study concomitant medical conditions*.

10.7 Previous and concomitant medication

Previous medications are defined as any medication with a start date prior to study start date [see definition in Section 10.2.1] and with an end date (last administration) prior to or equal to study start date.

Study concomitant medications are defined as any medication that is ongoing after informed consent signature date, or initiated at any time between study start and up to EOS [see definition in Section 10.2.6].

Study treatment concomitant medications at baseline (a subset of study concomitant medications) are defined as any medication with a start date before date of study treatment administration and is either ongoing at end of study or has a stop date after the study treatment administration date.

Study treatment concomitant medications (a subset of study concomitant medications) are any medications that are either ongoing at study drug administration or initiated within a 2-day period from study treatment administration, i.e., on the day and the following day of study drug administration.

If no end date is available for a medication, it is considered ongoing, and is therefore both a *study concomitant medication* and a *study treatment concomitant medication*.

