5.2 Previous and concomitant therapy

5.2.1 Definitions

A previous therapy is any treatment for which the end date is prior to signing of informed consent.

A therapy that is study concomitant is any treatment that is ongoing or initiated after signing of informed consent, or initiated up to 30 days after study treatment administration.

A therapy that is study treatment concomitant is any treatment that is either ongoing at the start of study treatment or is initiated up to 48 hours after study treatment administration.

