2.3 Overview of analysis periods

The study has 3 periods with regard to study drug administration:

1. *Baseline period*: from signature of informed consent to last moment prior to study drug administration.
2. *On treatment period*: from study drug administration and up to end of 48 hours (2 days) after study drug administration [see Section 10.1 for more details].
3. *Safety follow-up*: from the 49th hour for assessments with date/time, or from the third day for assessments with date only, after study drug administration and up to the end of the study.

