7.2.1.2 Treatment-emergent adverse events

Treatment-emergent AEs (TEAEs) are those AEs with onset date/time \geq date/time of study drug administration and \leq 48 h after date/time of study treatment administration.

AEs for which time of onset is missing will still be counted as treatment emergent if onset date is \geq date of study drug administration and is \leq date of study treatment administration +2 days.

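### SAP 10.7 misstates which drugs started after the injection count as study-treatment concomitant: the start window stops short of 48 h, and a missing end date removes the start-date limit

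*SAP*

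**What the plan says.** Protocol 5.2.1 defines study-treatment concomitant therapy as treatment that is "either ongoing at the start of study treatment or is initiated up to 48 hours after study treatment administration".

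SAP 10.7 keeps the part about drugs ongoing at the injection. For later starts it requires that the drug be "initiated within a 2-day period from study treatment administration, i.e., on the day and the following day of study drug administration". It then closes with a rule for missing end dates: "If no end date is available for a medication, it is considered ongoing, and is therefore both a" study concomitant and a study-treatment concomitant medication. That sentence sets no condition on the start date.

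Elsewhere the SAP turns the same 48 h into calendar days differently. SAP 2.3 runs the on-treatment period "from study drug administration and up to end of 48 hours (2 days) after study drug administration". SAP 10.1 says that, where only the day is known, this period "corresponds to the day of study drug administration and to the two following days (1st, 2nd and 3rd day of the on-treatment period"). SAP 7.2.1.2 counts an AE with no onset time as treatment-emergent up to the "date of study treatment administration +2 days".

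Protocol 5.2.2 lists start and end dates for medications, plus items for whether the drug was ongoing at the start of treatment and at End-of-Study. It lists no clock times. SAP 5.4.5 plans an incidence table of study-treatment concomitant medications by ATC code and INN. SAP section 11 does not mention any departure from protocol 5.2.1.

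**The concern.** The class is meant to show what subjects were taking around a single injection. As worded, it can err in opposite directions.

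- **Too narrow.** A short course begun on the morning of Day 3, for example for a bleeding event, is not counted even when it began within 48 h. The event itself would be counted as treatment-emergent. The AE table and the medication table would then use different calendar windows for the same 48 h.
- **Too wide.** A long-term drug begun well after the injection and still in use at the final call has no end date and enters the class. Protocol 5.2.4 restricts anticoagulants and new oral P2Y₁₂ antagonists only up to the last PK or PD sample, which Table 3 schedules at 24 h. A later start that the protocol permits could therefore look like an overlap with treatment.

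**Working it through.** The plan states no figure to reproduce. The check compares the definitions and then classifies test cases.

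**1. Length of the start window.** Let *h* be the clock hour of the injection on Day 1. The documents do not give it, so 08:00 to 16:00 is an assumption.

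- Protocol 5.2.1: window ends 48 h after the injection.
- SAP 10.7: window ends at midnight closing Day 2, which is 48 − *h* hours after the injection. Part of the 48 h not covered: *h* hours, or *h*/48.
- SAP 10.1 date-only convention: window ends at midnight closing Day 3, which is 72 − *h* hours after the injection.

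| Injection (assumed) | SAP 10.7 covers | Not covered | Share of 48 h | SAP 10.1 convention covers |
|---|---|---|---|---|
| 08:00 | 40 h | 8 h | 17% | 64 h |
| 10:00 | 38 h | 10 h | 21% | 62 h |
| 12:00 | 36 h | 12 h | 25% | 60 h |
| 14:00 | 34 h | 14 h | 29% | 58 h |
| 16:00 | 32 h | 16 h | 33% | 56 h |

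The two-day window is shorter than 48 h at every time shown, and the three-day convention always contains 48 h. The percentages are shares of hours, not of drugs or subjects.

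**2. How far the missing-end-date rule reaches.** SAP 10.7 admits study concomitant medications begun up to End-of-Study. Protocol 7.1 places that contact 30–37 days after the injection; protocol 5.2.1 stops at starts within 30 days. Because the last sentence has no start-date test, it reaches as far as medications are recorded. Appendix D treats a missing medication end date as ongoing and adds no start-date test either.

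**3. Test cases, injection at 10:00 on Day 1 (assumed).** The SAP column reads 10.7 literally.

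| Start | End date | Protocol 5.2.1 | SAP 10.7 |
|---|---|---|---|
| Day 2 | Day 5 | in | in |
| Day 3, 08:00 (46 h) | Day 5 | in | **out** |
| Day 3, 08:00 (46 h) | none | in | in, by the last sentence |
| Day 15 | Day 20 | out | out |
| Day 15 | none | out | **in** |
| Day 30 | none | out | **in** |

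The two definitions disagree in two situations: a Day 3 start within 48 h that has an end date, and a later start that has none.

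**4. Where the class is used.** SAP 5.4.5 uses it for the incidence table. The antiplatelet background categories there use the separate at-baseline class, which requires a start before the dosing date. The PD response in SAP 6.8.1.1 uses no medication window. The per-protocol exclusion for starting or changing an oral P2Y₁₂ drug (Appendix B) uses deviation codes.

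**The case against.** **The Day 1–2 window has a source.** Protocol 3.1.1 defines the treatment period as Day 1 and Day 2 and starts follow-up on Day 3. The last PK and PD samples are due at 24 h ± 2 h, so a Day 3 start cannot affect any PK or PD result. This stands as an explanation and is a reason to rate the point low. It does not reconcile SAP 10.7 with protocol 5.2.1, which says 48 h, or with SAP 10.1.

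**The last sentence may be only a missing-data convention.** The paragraph above it requires a drug to be ongoing at the injection or begun in the window, and a drug with a known Day 15 start cannot have been ongoing on Day 1. The CRF also has separate ongoing items, so a missing end date may be meant as an unknown one. That is a fair guess at intent, but the text draws the conclusion without a start-date condition. The documents show no programming for this class, so how it was coded is unknown.

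**Stronger readings that the documents do not support.**

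- A reader might infer that the window is wrong at both ends. It is not: the rule for drugs ongoing at the injection agrees with the protocol, and both faults concern later starts.
- A reader might infer that every Day 3 start is lost. Under the literal text, a Day 3 start with no end date is brought back in.
- A reader might infer that treatments are hidden. SAP 5.4.5 lists all previous and concomitant medications, so any such drug can be found.
- A reader might take 17–33% as a rate of misclassified drugs. Those figures rest on assumed injection times, and with date-only data the lost hours cannot be observed for an individual drug.

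**Conclusion.** The point holds and is minor. SAP 10.7 sets a start window shorter than the protocol's 48 h and inconsistent with the SAP's own date-only rule. Its last sentence, read literally, contradicts the definition directly above it and protocol 5.2.1. The consequence is possible misclassification in the descriptive table of study-treatment concomitant medications: Day 3 starts within 48 h that have an end date are omitted, and later starts with no end date are added. The number of drugs or subjects affected cannot be estimated from the documents. No PD estimate or test, at-baseline medication class, per-protocol exclusion or medication listing depends on this rule. The conclusion rests on the literal text of SAP 10.7 and on medication timing being recorded by date, as protocol 5.2.2 indicates.

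**What to change.** In SAP 10.7, define a study-treatment concomitant medication as one that meets both conditions:

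- the start date is no later than the dosing date plus 2 days; and
- the drug was in use at or after dosing. That means an end date on or after the dosing date or, if the end date is missing, that a drug started before dosing is not shown as already stopped by the collected item on whether it was ongoing at the start of treatment.

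Limit the last sentence so that a missing end date makes a drug ongoing but does not alone make it study-treatment concomitant. Record the change in SAP section 11.

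Applied to the test cases, the Day 2 start and both Day 3 starts are in, and the Day 15 and Day 30 starts are out, as under the protocol.

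The cost is two lines of wording and the matching programming, with no new data. The downside is slight over-inclusion: starts late on Day 3 are counted although they fall after 48 h, by up to 24 − *h* hours (16 h for an 08:00 injection, 8 h for 16:00). SAP 10.1 already accepts this for other date-only data. One detail needs a decision: a drug stopped on the dosing date would fall in this class but not in the at-baseline class, which requires a stop after that date. The SAP should state whether that difference is intended.
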